#### Table 5 - Analyses of adverse events

Type of AE	MedDRA levels
Treatment emergent SAE related to IMP as per Investigator's judgment	Primary SOC and PT
Treatment emergent AESIs	AESI category and PT
TEAE leading to permanent study intervention discontinuation	Primary SOC and PT
	PT
TEAE leading to death (death as an outcome of the AE as reported by the Investigator in the AE page)	Primary SOC and PT
Pretreatment AE	Overview a
	Primary SOC and PT
Post-treatment AE	Overview a
	Primary SOC and PT

a Will include the following AE categories: any AEs, any severe (grade ≥3) AEs, any serious AEs, any AEs leading to death

#### Analysis of deaths

In addition to the analyses of deaths included in Table 5 the number (%) of participants in the following categories will be provided:

- Deaths during the TE, OL, and post-treatment periods
- Deaths in non-randomized/non-enrolled participants or randomized but not treated participants

#### Analysis of adverse events of special interest (AESIs)

Adverse events of special interest (AESIs) will be selected for analyses as indicated in Table 6. Number (%) of participants experiencing at least one event will be provided for each event of interest. Tables will be sorted as indicated in Table 4.

AESIs	Selection				
Pregnancy of a female participant or female partner of a male participant	Dedicated CRF page (AECAT="PREGNANCY DATA")				
Symptomatic overdose (serious or non-serious) with IMP	Dedicated CRF page (AECAT="OVERDOSE DATA"; must be symptomatic and related to IMP)				
Increase in ALT >3 x ULN (confirmed)	Dedicated CRF page (AECAT="ALT INCREASE DATA") and AESI marked "Y"				
ECG observation of atrial fibrillation or atrial flutter	CMQ30003 for selection and AESI check box marked				
Severe infection (NCI CTCAE Grade 3 or above), that may or may not meet seriousness criteria (eg, a Grade 3 opportunistic infection)	SOC of Infections and Infestations, Grade 3 or above and AESI marked "Y"				

#### Table 6 - Selections for AESIs

AESIs	Selection
Moderate or severe hemorrhagic events (NCI CTCAE Grade 2 or above), including, but not limited to, symptomatic bleeding, bleeding in a critical area or organ such as the CNS, or intraocular bleeding	SMQNAME='Haemorrhage terms (excl laboratory terms)" for selection, Grade 2 or above, and AESI marked "Y"
Thrombocytopenia, platelet count <75 x 10  /L	PT="Thrombocytopenia" and AESI marked "Y"

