8.3.9 Adverse event of special interest

Adverse event of special interest

An AESI is an AE (serious or nonserious) of scientific and medical concern specific to the Sponsor's product or program, for which ongoing monitoring and immediate notification by the Investigator to the Sponsor is required. Such events may require further investigation in order to characterize and understand them. Adverse events of special interest may be added, modified, or removed during a study by protocol amendment.

- Pregnancy of a female participant entered in a study as well as pregnancy occurring in a female partner of a male participant entered in a study with IMP/NIMP
 - It will be qualified as an SAE only if it fulfills one of the seriousness criteria (see Appendix 3 [Section 10.3]),
 - In the event of pregnancy in a female participant, IMP should be discontinued,
 - Follow-up of the pregnancy in a female participant or in a female partner of a male participant is mandatory until the outcome has been determined (See Appendix 4 [Section 10.4]).

- Symptomatic overdose (serious or nonserious) with IMP
 - An overdose (accidental or intentional) with the IMP is an event suspected by the Investigator or spontaneously notified by the participant (not based on systematic pills count) and defined as at least twice the intended dose within the intended therapeutic interval (eg, ≥2 tablets of the IMP within a 12-hour interval).
- Increase in alanine transaminase (ALT) >3 × ULN
 - ALT increase >3 × ULN confirmed by retest within 72 hours or in the absence of a retest within 72 hours.

• Other project specific AESI(s)

- ECG observation of atrial fibrillation or atrial flutter,
- Severe infection (NCI CTCAE Grade 3 or above) infection, that may or may not meet seriousness criteria (eg, a Grade 3 opportunistic infection),
- Moderate or severe hemorrhagic events (NCI CTCAE Grade 2 or above), including but not limited to symptomatic bleeding, bleeding in a critical area or organ such as the CNS, or intraocular bleeding,
- Thrombocytopenia, platelet count <75 000/mm³ (see Appendix 6 [Section 10.6] for management flow chart).

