10.3.1 Definition of AE

AE definition

- An AE is any untoward medical occurrence in a patient or clinical study participant, temporally associated with the use of study intervention, whether or not considered related to the study intervention.
- NOTE: An AE can therefore be any unfavorable and unintended sign (including an abnormal laboratory finding), symptom, or disease (new or exacerbated) temporally associated with the use of study intervention.

Events meeting the AE definition

- Any abnormal laboratory test results (hematology, clinical chemistry, or urinalysis) or other safety assessments (eg, ECG, radiological scans, vital signs measurements), including those that worsen from baseline, considered clinically significant in the medical and scientific judgment of the Investigator (ie, not related to progression of underlying disease), eg:
 - Symptomatic and/or
 - Requiring either corrective treatment or consultation, and/or
 - Leading to IMP discontinuation or modification of dosing, and/or
 - Fulfilling a seriousness criterion, and/or
 - Defined as an AESI.
- Exacerbation of a chronic or intermittent pre-existing condition including either an increase in frequency and/or intensity of the condition.
- New conditions detected or diagnosed after study intervention administration even though it may have been present before the start of the study.
- Signs, symptoms, or the clinical sequelae of a suspected drug-drug interaction.
- Signs, symptoms, or the clinical sequelae of a suspected overdose of either study intervention or a concomitant medication.
- "Lack of efficacy" or "failure of expected pharmacological action" per se will not be reported as an AE or SAE. Such instances will be captured in the efficacy assessments. However, the signs, symptoms, and/or clinical sequelae resulting from lack of efficacy will be reported as AE or SAE if they fulfil the definition of an AE or SAE.

Events NOT meeting the AE definition

- Any clinically significant abnormal laboratory findings or other abnormal safety assessments which are associated with the underlying disease, unless judged by the Investigator to be more severe than expected for the participant's condition.
- The disease/disorder being studied or expected progression, signs, or symptoms of the disease/disorder being studied, unless more severe than expected for the participant's condition.

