10.6 APPENDIX 6: LIVER AND OTHER SAFETY: ACTIONS AND FOLLOW-UP ASSESSMENTS

These actions are required for ALT increase and thrombocytopenia events ONLY. For all other safety events described, these are suggested per the Investigator's medical judgement.

[figure not shown]

- 3. **INFORM** the local monitor
- 4. **INVESTIGATE** previous treatments particularly long-term, even a long time ago, exposure to toxic agents, e.g., benzene, X-rays, etc.
- 5. **PERFORM** and collect the following investigations (results):
 - RBC and platelet counts, Absolute Neutrophil Count (ANC)
 - Infectious serologies to be performed locally, according to clinical symptoms / medical history
- 6. **DECISION** for bone marrow aspiration: to be taken in specialized unit
- 7. COLLECT/STORE one sample following handling procedures described in PK sections (for studies with PK sampling)
- 8. MONITOR the leukocyte count 3 times per week for at least one week, then twice a month until it returns to normal

* For individuals of African descent, the relevant value of concern is <1000/mm³

Neutropenia is to be recorded as an AE only if at least 1 of the criteria listed in the general guidelines for reporting AEs in Appendix 3 (Section 10.3) is met.

THROMBOCYTOPENIA

Abbreviations: aPTT: activated partial thromboplastin time; EDTA: Ethylenediaminetetraacetic acid; INR: international normalized ratio; PK: pharmacokinetic; PT: prothrombin time

[figure not shown]
Thrombocytopenia is to be recorded as an AE only if at least 1 of the criteria listed in the general guidelines for reporting AEs in Appendix 3 (Section 10.3) is met.

LIVER FUNCTION TEST MONITORING ADDITIONAL GUIDANCE:

To allow timely review for these data, please enter the date of collection for the central lab and the date of collection and the results for the local lab in the eCRF within 24 hours of their availability.

- 1. If 1 LFT monitoring timepoint is missed, the study site should:
 - Reach out to the study participant as soon as possible to schedule an alternative timepoint as soon as possible and prior to the next scheduled timepoint.
 - Retrain the study participant on the LFT monitoring rationale and requirements and inform the study participant that IMP will need to be interrupted if LFTs cannot be monitored as required.
- 2. If 2 consecutive LFTs timepoints are missed, the site should:

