10.14.4 Amended protocol 04 (26 July 2021)

This amended protocol (amendment 04) is considered to be substantial based on the criteria set forth in Article 10(a) of Directive 2001/20/EC of the European Parliament and the Council of the European Union.

OVERALL RATIONALE FOR THE AMENDMENT

The primary reason for this amendment is the availability of new information from drug-drug interaction studies.

Section # and Name	Description of Change	Brief Rationale
Synopsis 3 Objectives and endpoints	Changed a secondary endpoint from "Change in lymphocyte phenotype subsets in whole blood at the EOS compared to baseline" to "Change in lymphocyte phenotyping subsets in whole blood at the EOS compared to baseline in a subset of participants."	Lymphocyte phenotyping will be assessed only for participants who were sampled before implementation of amended protocol 04.
1.3 Schedule of Activities, footnotes	The footnotes were updated as follows:	
	 Footnote a: To allow a window of 1 additional week (7 days) for screening magnetic resonance imaging (MRI) if required to be rescheduled or repeated (eg, in case of technical issues). 	To allow more flexibility for screening MRI and safety laboratory tests.
	• Footnote d: To allow safety laboratory tests at Months 1, 2, 4, and 5 to be done locally if either onsite visit or home health visit is not possible.	To allow more flexibility for the laboratory test assessment.

Protocol amendment summary of changes

Section # and Name	Description of Change	Brief Rationale
	 Footnote e: To clarify the study procedures/assessments to be performed if a participant prematurely permanently discontinues treatment with the IMP. 	Clarity.
	 Footnote i: Text added: Screening tests for TB are described in Appendix 2 (Section 10.2). 	Clarity.
	 Footnote k: Text added: Lipase will be tested at the Screening Visit, then quarterly. Also clarified that additional safety assessments can be performed at local laboratories, if required by local regulations. 	Clarity.
	 Footnote I: Text updated as: A serum ß-hCG pregnancy test will be analyzed at a central laboratory at screening and urine pregnancy tests before the first dose of investigational medicinal product (IMP) and at scheduled times during the study. 	Clarification of pregnancy tests required during the study.

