	To add collection of a pharmacokinetic sample at premature end of treatment (pEOT) visit, if the visit can be scheduled within a maximum 24 hours from the last IMP dose.	To clarify that the PK sample should be collected in case of pEOT only if the visit can be scheduled within 24 hours due to short $t_{1/2}$ after the last IMP dose.

Section # and Name	Description of Change	Brief Rationale
7.1.2 Temporary discontinuation	Text updated to clarify contingency measures in case of temporary intervention discontinuation because of AEs or regional or national emergency declared by a government agency.	Clarity.
8.1.2 Magnetic resonance imaging	Increased the MRI test time from 21 days to 1 month following last course of systemic corticosteroids.	To be consistent with screening MRI requirement and to minimize the risk of corticosteroid impact on MRI findings.
8.1.3.1 Definition of multiple sclerosis relapse	Clarified that MS relapse confirmation will be done by the Relapse Adjudication Committee.	Clarity.
8.2.2 Vital signs	Clarified that blood pressure and heart rate measurements will be assessed in a supine or sitting position	Clarity.
8.2.3 Electrocardiograms	Added allowance of manual calculation of QT interval corrected using Fridericia's formula (QTcF).	To allow some flexibility as some automated electrocardiograms do not provide these parameters. All other electrocardiogram parameters will be automatically provided.
8.3.8 reporting of safety findings from magnetic resonance imaging	Text updated to "In case of clinically relevant findings, relevant information needs to be provided to the Treating Investigator for appropriate safety reporting and also to ensure the appropriate management of the participant's identified safety finding."	Clarity.
8.3.9 Adverse events of special interest	Definition of overdose was clarified.	Clarity.
	Definition of project-specific adverse events of special interest related to infection and hemorrhagic events was updated.	Clarity for the infection and hemorrhagic events to be reported as adverse events of special interest.
	Thrombocytopenia, platelet count updated from <100 000/mm ³ to <75 000/mm ³	Modified to align with CTCAE guidelines for thrombocytopenia
8.4 Treatment of overdose	Corrected the language to clarify that plasma sample for PK analysis is to be obtained within 24 hours of the last documented IMP dose (rather than the last dose of SAR442168).	Correction of error.

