## **VERSION HISTORY**

This amended statistical analysis plan (SAP) for study EFC16645 is based on the amended protocol 11 dated 20 November 2023. The first participant was randomized on 23 October 2020. The initial SAP V1 was approved before the interim analysis for futility was conducted. Amended SAP V2 reflected statistical section changes incorporated in amended protocol 10 versus amended protocol 8 and any major changes since amended protocol 10. This amended SAP specifies rule for imputation of missing baseline Gd-enhancing T1-hypertintense lesion presence or absence status and additional analyses to support integrated safety summary.

SAP Version	Approval Date	Changes	Rationale
1	10-Feb-2023	Original version changes from protocol amendment 8	
		More covariates, ie, baseline EDSS score and Gd- enhancing T1 lesions at baseline are specified in the Cox model for the primary endpoint and other related time-to-event endpoints	Based on clinical input
		Censoring approach is different: imputation of 6-month confirmation event status is performed only for participants who have an initial onset of disability progression but complete the study at the common study end date with 3-month confirmation and without 6-month confirmation.	Based on FDA feedback
		For subgroup analysis of prior therapy use, the categories are 0, 1, $\geq 2$	Clarification
		Actigraphic analysis baseline is defined at time of enrollment in substudy	Clarification
2	30-Oct-2023	Changes already incorporated in Amended protocol 10:	Based on FDA feedback
		Update the imputation approach for primary analysis: imputation of 6-month confirmation event status is performed only for participants who meet 3-month CDP criteria and continue to meet the criteria for EDSS disability progression through the final study assessment, but do not reach 6-month confirmation.	
		Changes from Amended protocol 10:	Clarification
		Change offset variable for analysis of new/enlarging T2 lesions to time from screening MRI to last available MRI scan rather than observation duration.	

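### SAP Table 6 selects the thrombocytopenia AESI by one coded term plus a flag, without a platelet value, so the row can depart from its own <75 x 10^9/L label; the flag can also remove qualifying hemorrhages

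*SAP*

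**What the plan says.** Protocol section 8.3.9 defines this AESI by a laboratory number: "Thrombocytopenia, platelet count <75 000/mm³". SAP section 3.6.2, Table 6, repeats the number in the row label (as 75 x 10^9/L) but selects participants by "PT='Thrombocytopenia' and AESI marked 'Y".

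The number changed during the trial. The log for Amended Protocol 04 (Protocol section 10.14.4, 26 July 2021) has an entry for section 8.3.9 beginning "Thrombocytopenia, platelet count updated from <100 000/mm", which records the move to 75 000/mm3. The SAP version history states: "The first participant was randomized on 23 October 2020". So enrollment began under the higher threshold.

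On recording, Protocol Appendix 6 says: "Thrombocytopenia is to be recorded as an AE only if at least 1 of the criteria listed in the general guidelines for reporting AEs". One of those criteria, in section 10.3.1, is "Defined as an AESI". A count below the current threshold should therefore reach the AE page.

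Protocol section 8.3.9 defines the hemorrhage AESI by event type and Grade 2 or above. Table 6 uses the standardized hemorrhage query (SMQ) "for selection, Grade 2 or above, and AESI marked 'Y". The infection row is built the same way, from the Infections system organ class (SOC), Grade 3 or above, and the flag.

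**The concern.** A row defined by a laboratory value should count participants with that value. Here the count depends on which preferred term the event was coded to and whether a box was ticked, and the instruction behind the box changed after randomization had begun. The row can then be wrong in both directions even where sites followed the protocol in force at the time.

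AESIs are a listed secondary safety endpoint, and SAP Appendix 5 carries them into relative-risk and risk-difference forest plots. Protocol section 2.3 names cytopenia including thrombocytopenia, and bleeding, as potential risks. A reader of those plots would take the label at face value.

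**Working it through.** **Units.** 75 x 10^9/L = 75 000/mm3, so the SAP label and the current protocol agree. The earlier threshold equals 100 x 10^9/L.

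**The rule against the label.** Take one count below 75 and one between 75 and 100 (x 10^9/L):

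| Platelets | Coded term | Flag | Meets <75 label | Selected by Table 6 |
|---|---|---|---|---|
| 60 | Thrombocytopenia | Y | yes | yes |
| 60 | Thrombocytopenia | N | yes | no |
| 60 | other low-platelet term | Y | yes | no |
| 90 | Thrombocytopenia | Y | no | yes |
| 90 | Thrombocytopenia | N | no | no |

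Row 4 needs no site error if the flag was set under the earlier threshold. Row 3 needs no site error either, only a different coded term. Row 2 needs a missed flag.

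**How long the earlier threshold applied.** 23 October 2020 to 26 July 2021 is 276 days; 276/28 = 9.9 months by the trial's 28-day convention. This is a minimum, since sites may have adopted the amendment later.

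**Exposure in that window.** The scheduled post-baseline hematology target days in SAP Table 8 up to day 276 are 28, 56, 84, 112, 140, 168 and 252, which is 7. Adding 336, 420, 504, 588 and 672 gives 12 to Month 24. So 7 of 12 is the most that could fall in the window, and only for someone randomized at the very start.

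An average needs assumptions. Take uniform enrollment over the planned 24 months (24 x 28 = 672 days) and the protocol's estimated mean treatment duration of 33 to 36 months (924 to 1008 days):
- Share randomized before the amendment: 276/672 = 41%, with a mean of 276/2 = 138 days in the window.
- Share of all treatment time: 0.41 x 138 = 57 days per randomized participant; 57/1008 to 57/924 = about 6%.
- With a 90-day adoption lag (assumed): 366/672 = 54%, mean 183 days, about 100 days; 100/1008 to 100/924 = about 10 to 11%.

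**Effect of one misclassified participant**, using randomized numbers in place of the safety population, at 2:1:
- 1290 randomized: 860 and 430; 1/860 = 0.12 points, 1/430 = 0.23 points.
- 1100 randomized: 733 and 367; 1/733 = 0.14 points, 1/367 = 0.27 points.

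These are units of change, not estimates. The documents give no rate of low platelets, coding to other terms, or flagging.

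**Hemorrhage and infection.** In both rows the flag is a further AND condition on type and grade, so it can only remove events. For infection, SAP Table 5 already tabulates Grade 3 or above treatment-emergent events by SOC, so the flag-free count can be read from its Infections row. No planned table is specified to give hemorrhage by SMQ and Grade 2 or above without the flag.

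**Other outputs.** The analyses of potentially clinically significant abnormalities (PCSA, SAP section 3.6.3.1) use all local and central platelet values, but take their cut-offs from a company list that the plan does not reproduce. Whether they count platelets below 75 cannot be told. The detailed AESI summaries in Appendix 5 have no stated layout.

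**The case against.** The strongest reply is that the flag is not empty. An AESI is an investigator-reported AE, the protocol gives the investigator the numerical criterion, and the flag is how that criterion enters the selection. A reader might infer that the plan ignores its own threshold altogether. The documents do not support that: for events flagged under Amended Protocol 04 or later, the flag carries the current criterion. What remains is the period before it, and events coded to another term. The protocol provides for source verification and sponsor quality checks, with monitoring details held elsewhere, but neither document states a rule for checking flags against platelet values.

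Second, the over-count needs several things together: an early participant, a count of 75 to 100, a flag, and no later correction. Entry required at least 150 000/µL, so reaching 100 means a fall of a third (50/150). This stands as a limit on size. It would be wrong to take 7 of 12 counts as typical.

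Third, a reader might infer that severe infections are lost in the same way. They are not lost to the report, because Table 5 supplies the flag-free count.

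Fourth, the ALT row has the same form. However, the SAP separately analyzes ALT above 3 x ULN from laboratory values, which it does not do for platelets at 75. The atrial fibrillation and flutter row also uses the flag, but that AESI is an ECG observation, which a term search alone does not establish.

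Fifth, it is tempting to replace the row with any platelet value below 75. That changes what is counted: AESIs are AEs tabulated by preferred term, and a bare laboratory value has none. This objection stands, and the fix keeps the AE row.

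**Conclusion.** The point holds as a minor one. The thrombocytopenia row does not guarantee what its label states. Followed exactly, the rule can include events at 75 to 100 x 10^9/L flagged under the earlier threshold and omit events below 75 coded to another term. The hemorrhage row can omit events that meet the protocol definition.

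The amendment log is used only as evidence of how early flags were set. The current protocol and the SAP label agree, and nothing here bears on which threshold is clinically appropriate.

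The consequence is confined to descriptive AESI incidence and the Appendix 5 relative risks and risk differences. Safety is not tested, and the primary analysis, type 1 error and power are untouched. The direction is not fixed, and the size is unknown and possibly zero. The conclusion assumes that no unseen reconciliation step has already corrected the early flags.

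**What to change.** 1. Keep the thrombocytopenia row in Table 6 based on AEs, but accept any low-platelet AE term, with the terms listed. Count a flagged event under the label only if its recorded platelet value is below 75 x 10^9/L, or if no value is available.
2. Beside it, give the number and percentage of participants by arm with any treatment-emergent platelet count below 75 x 10^9/L, central or local. Add a listing of repeat values and of mismatches with flagged events, marking flags set under the earlier threshold.
3. Report hemorrhage by the SMQ and Grade 2 or above, with and without the flag. Cross-refer the infection row to the Grade 3 or above Infections SOC count in Table 5.

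The cost is a change to SAP wording, minor programming and some reconciliation, on data already collected. AESI counts may shift slightly. A single spurious platelet value could enter the laboratory count, and the listing of repeat values would expose it.
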